9.4 Safety Analyses

- We shall continuously monitor and document all serious adverse events (SAEs), categorizing them by severity, causality, and timing relative to the intervention. This includes both anticipated events related to cancer and potential unexpected events related to the intervention.
- Comparative Analysis: Compare the incidence rates of SAEs between the intervention and control groups. This can help ascertain whether the intervention group experiences a higher rate of events, indicating potential safety concerns.
- The Trial Monitoring Committee shall regularly monitor these and can decide to forfeit the trials when there are clear indications that safety of the survivor is in danger due to our intervention
- Along with that we shall utilize QoL and well-being measures to indirectly assess safety, as significant declines could indicate adverse impacts of the intervention.

9.5 Other Analyses

- Futility Analysis: will be assessed to the inability of the clinical trial to achieve the primary and secondary objectives. In that case, both operational and statistical futility will be analyzed. Operational futility includes slow recruitment or slow accumulation of primary endpoints. Statistical futility includes, for the most part, group sequential methods and conditional power.

9.6 Interim Analyses

- Interim analyses are planned to evaluate the primary and secondary objectives' safety and efficacy data. These analyses may also explore data trends that could necessitate adjustments to the trial conduct.
- Statistical Methods:

- The interim analyses will employ group sequential testing methods with an O'Brien-Fleming spending function to rigorously control the type I error rate across multiple looks at the data.
- Execution:
 - The analyses will be performed by an independent biostatistician from the trial investigators to maintain objectivity.
- Timing and Triggers
 - Scheduled Interim Analyses: Interim analyses are planned at 3 months, 6 months and 12 months of trial commencement.
 - Ad Hoc Requests: Additional interim analyses may be conducted at the request of the Trial Monitoring Committee, particularly if unexpected safety concerns arise.
- Decision Criteria and Oversight
 - Decision Criteria: The criteria for early stopping or trial adaptation include a pre-specified boundary for efficacy (significant reduction in healthcare expenditure or improvement in health outcomes) or safety concerns (unacceptable adverse events rate).
 - The Trial Monitoring Committee will oversee the interim analyses, reviewing the results to make recommendations on continuing, stopping, or modifying the trial.
 - Blinding Integrity: Individuals analyzing the data may have access to unblinded data; however, measures will be taken to ensure that the trial team remains blinded to maintain the integrity of the trial implementation.
 - Authority to Stop or Modify: The ultimate authority to stop or modify the trial rests with the TMC, in consultation with the principal investigator and the sponsor, based on the interim findings and established stopping guidelines.

9.7 Sample Size Determination

- The metric-wise sample size calculation is provided in the table below on alpha as 0.05 and power of 80% for the one-tail test at enrollment ratio = 1.

- While we are conducting the power analysis and sample size calculation based on several variables (outcomes) of interest, the sample size was computed separately for each parameter in the study and the greatest is used to obtain sample size.
- The analysis (detailed below in table) showed that sample of size of 102 is powerful enough for the analysis to cover 100% of primary and secondary metrics.
- Now since we believe that the long follow-up duration of 12 months for our trial will lead to around 30% drop-offs, we decided a final sample size of 146 (73 control, 73 test).
- So even if get 30% or 44 participants drop off we end up with final sample set of 102 (51 control, 51 test) and would be able to come to statistically significant effects ($p < 0.05$) with respect to 100% of primary and secondary metrics.

Metric Segment	Sub Metric	Control Data	Test Data	Assumed Variance	Sample Size
Primary Outcome / Concerns					
Medical Expenditure	Total Healthcare Expenditure (Planned + Unplanned)	10000	8000	Variance of 4000	102 (51 Control, 51 Test)
	No of Urgent Care Visits	3	2.5	Variance of 0.5	28 (14 Control, 14 Test)
	No of ED Visits	5	3.45	Variance of 0.8	10 (5 Control, 5 Test)
	No of unplanned outpatient/office	4.28	3.5	Variance of 0.8	28 (14 Control, 14 Test)

	visits (other than ED)				
	Unplanned Hospitalisations	5	4	Variance of 0.8	18 (9 Control, 9 Test)
	Length of hospital stay	3	2	Variance of 0.8	18 (9 Control, 9 Test)
	No of planned outpatient visits	2	1.8	Variance of 0.3	58 (29 Control, 29 Test)
	No of planned hospital visits	1.25	1	Variance of 0.1	10 (5 Control, 5 Test)
	Length of hospital stay	3	2	Variance of 0.8	18 (9 Control, 9 Test)
	Total Prescription Medicine Expenditure	1000	950	Variance of 80	80 (40 Control, 40 Test)
Secondary Outcome / Concerns					
Adherence	MMAS scale	4.5	7	Variance of 2.5	28 (14 Control, 14 Test)
QoLS Score, Pain Levels, Sleep Quality, Physical Activity	QoLS Score (FACT-G)	70	85	Variance of 20	42 (21 Control, 21 Test)
	Brief Pain Inventory (Short Form)	80	60	Variance of 35	78 (39 Control, 39 Test)

	PROMIS (Short Form)	70	55	20	46 (23 Control, 23 Test)
	GLTEQ	25	17	10	42 (21 Control, 21 Test)
	Calorie Burnt	120	198	Variance of 70	22 (11 Control, 11 Test)
Presenteeism	Attitude towards work	2	4	Variance of 1.5	16 (8 Control, 8 Test)
	Employee Performance	0.6	0.7	Variance of 20%	102 (51 Control, 51 Test)
Cancer Care	Cancer Progression Status	0.85	0.88	Variance of 0.04	46 (23 Control, 23 Test)
	Cancer recurrence status	0.3	0.21	Variance of 10%	32 (16 Control, 16 Test)
Absenteeism	Working Hours	30	40	Variance of 10	28 (14 Control, 14 Test)
	Vacation Days	0.5	0.3	Variance of 0.15	16 (8 Control, 8 Test)

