1.1 Protocol Synopsis

- **Primary and Secondary objectives and endpoints**

- Primary Objective - To quantify the impact of Complement Theory's Program on total healthcare expenditure in cancer survivors. This includes assessing both cancer-related and non-cancer-related costs, further categorized into planned and unplanned expenditures.
- Secondary Objectives:
 - Evaluate the effects of CT's Digital Application Program on adherence to treatment (using MMAS-8 survey)
 - Measure the program's influence on Quality of Life, Physical Activity, Sleep Quality and Pain levels of participants.
 - Quantify the effect of CT's program on employee absenteeism by tracking changes in the number of sick days taken by participants.
 - Determine the program's impact on employee presenteeism by assessing changes in work motivation and employee performance review scores.
- Exploratory Objective
 - Assess the impact of CT's Program on the progression and recurrence rates of prostate, colorectal, and lung cancers, by evaluating changes in tumor size and biomarker levels, including Blood pressure, PSA or protein, in addition to monitoring actual recurrence rates.

- **Overall Design**

- Several key aspects of the trial design are summarized below:

Trial Model	Randomized control trial with two parallel groups: one active comparator (control) and one test group.
-------------	--

[figure not shown]
Test Intervention	Live 1:1 Coaching program, focusing on Exercise and Meditation, along with app-guided evidence-based information on Diet, Sleep, and other lifestyle practices for 24 weeks
Active Comparator (Control)	24 weeks access to Digital application with expert guidelines on lifestyle modification focusing on exercise, meditation, as well as information on diet, sleep and other lifestyle practices. Does not include live coaching and personalization.
Trial Intervention Assignment Method	Randomization
Population Type	Adult survivor
Population Diagnosis	Active Cancer (Breast, Prostate, Colorectal, Lung and Other) Stage 1-4
Population Age	21 to 64 yrs
Site Distribution	Digital Recruitment of participants who can be anywhere in the US

- **Number of Arms**
 - Two - One active comparator (control) and one test
- **Blinding**
 - The study will be double-blind: Participants and the Principal Investigator will not be made aware of treatment assignment.
 - Both the groups shall be given access to the app. The contents shall be different for active comparator and the test group.

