2.1 Purpose of Trial

The randomized controlled trial (RCT) aims to evaluate the efficacy of Complement Theory's (CT) personalized and interactive, evidence-backed lifestyle program in reducing healthcare costs and improving health outcomes for survivors across all major cancer types.

Distinct from conventional interventions, CT's program offers live 1:1 coaching through a mobile app, concentrating on Exercise and Meditation, and is enriched with evidence-based advice on Diet, Sleep, and comprehensive lifestyle modifications. This trial is pivotal in assessing the program's effectiveness against an active comparator—expert-recommended lifestyle modification resources suitable for cancer survivors—to isolate the impact of coaching and personalization.

The primary objective is to investigate whether CT's novel approach can more effectively reduce healthcare utilization, through reduction of hospitalizations, urgent care visits, and outpatient visits. Furthermore, the trial seeks to measure adherence to treatment, and significant health outcomes, including improvements in Quality of Life Scores (QoLS) to provide a holistic evaluation of the program's impact on patient care and well-being. As an exploratory effort, the trial will also measure cancer progression, recurrence in Prostate and Colorectal cancer survivors alone.

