9.2 Analyses Supporting Primary Objective(s)

- The primary analysis will focus on quantifying the impact on total healthcare expenditure including hospitalization costs, medication expenses, outpatient visits, and any other related healthcare services over the trial period.
- We will try to establish the efficacy of Complement Theory by measuring the difference in mean total healthcare expenditure between the intervention and control groups at 3, 6, and 12 months and 18 months from baseline.
- **Statistical Model, Hypothesis, and Method of Analysis**
 - Primary Estimand (Healthcare Expenditure Reduction):
 - Null Hypothesis (H0): There is no difference in healthcare expenditure between participants in the Complement Theory program and those in the control group.
 - Alternative Hypothesis (H1): Participants in the Complement Theory program exhibit a significant reduction in healthcare expenditure compared to the control group.
 - Baseline Data Analysis: Baseline demographics and characteristics will be provided and summarized in both treatment and control groups. Standardized mean differences (SMDs) will be calculated as the measure of distance between groups. SMDs of 0.2 to <0.5, 0.5 to <0.8 and ≥ 0.8 are considered small, medium, and large, respectively. Frequencies and percentage will be provided for the binary variables as well as the

categorical variables (Yes/No); mean (standard deviation) and median (range) will be computed for continuous variables.

- Method of Analysis: A Generalized Linear Model (GLM) with an appropriate link function and distribution family that best fits the distribution of healthcare expenditure data. Both univariate and multivariate analyses will be conducted. The method will capture the effect on the outcome in treatment and control group from each independent variable. In addition, the strength of the effect from each of the variables would be evaluated through the statistical test significance, i.e., P value, at 95% confidence interval.
- **Handling of Intercurrent Events of Primary Estimand(s)**
 - For participants who discontinue the intervention or are non-adherent, we will employ a treatment policy strategy. This means all data collected will be analyzed as per the initial treatment assignment, regardless of the discontinuation or level of adherence, preserving the intention-to-treat principle.
- **Handling of Missing Data**

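### The Combined protocol and SAP names total expenditure as primary, but its sample-size table lists ten primary rows at full alpha, no time point is decisive, and its claim to cover 100% of metrics holds only metric by metric

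*Combined protocol and SAP*

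**What the plan says.** All references are to the Combined protocol and SAP unless stated.

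- **Endpoint.** Sections 1.1, 3 (Trial Objective 1), 3.1 and 9.2 make total healthcare expenditure primary, and the hypotheses in 9.2 concern nothing else. Section 9.1 assigns the ITT set to the primary analysis of expenditure, but mentions cancer progression in the same sentence. Section 1.1 adds splits: "This includes assessing both cancer-related and non-cancer-related costs, further categorized into planned and unplanned expenditures". Section 2.1 puts the primary objective differently, as whether the program can "reduce healthcare utilization, through reduction of hospitalizations, urgent care visits, and outpatient visits".
- **Time.** Section 9.2 measures the "difference in mean total healthcare expenditure between the intervention and control groups at 3, 6, and 12 months and 18 months from baseline". No time is named as decisive.
- **Sample size.** The 9.7 table has ten rows under "Primary Outcome / Concerns": total expenditure, prescription expenditure and eight utilization rows. Length of hospital stay appears twice, so there are nine distinct labels. The calculation is "on alpha as 0.05 and power of 80% for the one-tail test at enrollment ratio = 1", and "the sample size was computed separately for each parameter in the study and the greatest is used to obtain sample size". The text concludes that a "sample of size of 102 is powerful enough for the analysis to cover 100% of primary and secondary metrics", then repeats this as an expectation of p < 0.05 on all of them after dropout.
- **Error control.** Section 9.6 applies an O'Brien-Fleming spending function over looks at 3, 6 and 12 months from trial commencement. Its efficacy criterion is met by reduced expenditure or, alternatively, by better health outcomes, which are not defined. No section controls error across metrics.

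**The concern.** A primary analysis needs one contrast, fixed in advance, that decides success. Here the objective and hypotheses point to total expenditure, Section 2.1 points to utilization, and the 9.7 table labels ten rows as primary. The rows can disagree: unplanned visits may fall while total cost does not. With no hierarchy and no decisive time, a report could choose which primary row or time to present as the result. The open-ended efficacy criterion in 9.6 leaves the same latitude at an interim look.

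The 100% sentence is a second problem in the same section. Sizing on the most demanding row gives each metric at least 80% power. It does not give 80% power, let alone assurance, that all metrics are significant together.

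**Working it through.** **1. Reproduce the plan's figure.** Inputs from 9.7: means 10000 and 8000, "Variance of 4000", one-sided alpha 0.05, power 80%, 1:1 allocation.
- Normal approximation with 4000 read as an SD: n per arm = 2 × (1.645 + 0.842)² × 4000² / 2000² ≈ 49.5, so 50.
- Noncentral t: power is 0.799 at 50 per arm and 0.806 at 51, so 51 per arm, or 102. This matches.
- With 4000 read as a true variance, n is 1 per arm. The plan's figure is therefore recovered only if the stated variance is an SD, and the rest of this check reads the table that way.
- Dropout: 102 / 0.7 = 145.7, so 146. This matches.
- Eight of the ten primary rows reproduce. Planned hospital visits (5 stated, 3 computed per arm) and prescription expenditure (40 stated, 33 computed) do not. Neither drives N.

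**2. False-positive rate if any of the ten rows could count as success.** One analysis time, one-sided 0.05 each.
- Independent rows: 1 − 0.95¹⁰ = 0.401.
- Common correlation ρ: 1 − ∫ Φ((1.645 − √ρ·u)/√(1 − ρ))¹⁰ φ(u) du. The documents give no correlation, so ρ is an assumption.

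| ρ | ten rows | nine distinct labels |
|---|---|---|
| 0 | 0.401 | 0.370 |
| 0.3 | 0.307 | 0.288 |
| 0.5 | 0.247 | 0.233 |
| 0.7 | 0.185 | 0.177 |
| 0.9 | 0.115 | 0.112 |

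**3. Total expenditure alone at four times.** Assume cumulative cost with independent increments, so that the correlation between times s < t is √(s/t). Simulating the four tests at 3, 6, 12 and 18 months, each at one-sided 0.05, gives 0.126. This applies only if the spending function is not applied to these contrasts. If it is applied, the rate is 5%.

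**4. Joint power with 51 per arm.** For each row, d = absolute difference / stated variance read as SD. Power comes from the noncentral t with 100 degrees of freedom and noncentrality d·√(51/2).
- Total expenditure, d = 0.5: 0.806
- Prescription expenditure, d = 0.625: 0.932
- Planned outpatient visits, d = 0.667: 0.955
- Employee performance, d = 0.5: 0.806
- Brief Pain Inventory, d = 0.571: 0.889
- Every other row: at least 0.98

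For the ten primary rows if independent, 0.806 × 0.932 × 0.955 ≈ 0.717, and the other seven rows are so close to 1 that the product stays at 0.717. For all 22 rows (ten primary, twelve secondary), joint power is 0.48 if independent, 0.63 at an assumed correlation of 0.5, and 0.72 at 0.8.

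**5. The separate Protocol.** Its 9.7 table has one primary row (FACT-G) and four secondary rows. FACT-G has d = 15/20 = 0.75 and power 0.983, and employee performance has 0.806. The other three rows are near 1, so joint power if independent is about 0.983 × 0.806 ≈ 0.79.

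**The case against.** The strongest reply is that the primary endpoint is not in doubt. Objective, estimand and hypotheses all name total expenditure. The ten rows appear only in a sample-size table, as sub-metrics of medical expenditure, and Section 2.1 is narrative. This largely stands. A reader might infer that the ten rows are co-primary and that any one of them wins the trial, but no section states such a rule, and the hypotheses in 9.2 contradict it. What remains is a contradiction: a formal section labels the rows primary, another states utilization as the primary objective, and nothing ranks them.

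A reader might also take 25% as a minimum false-positive rate. It is not. It needs the any-row rule and an assumed correlation of 0.5, and at 0.9 the rate is about 12%. Several rows are components or drivers of total cost, so independence is a poor guide to the upper end. Testing all ten rows at all four times would give about 49% at correlation 0.5, but the plan contains no such forty-test rule.

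Nor is it right that repeated looks go uncontrolled. Section 9.6 specifies a spending function at nominally the same times as 9.2. What stands is narrower: 9.6 counts from trial commencement and 9.2 from baseline, the two are not linked, and the spending function does not cover several metrics or the undefined health-outcome criterion.

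Finally, the 100% sentence can be read as a claim about each metric separately. On the plan's inputs that reading is correct, since the lowest power is 0.806. The sentence does not say so, and the text that follows reads as an expectation for all metrics together.

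**Conclusion.** The point holds as an unresolved contradiction plus an overclaim about power. It does not show that the plan adopts an inflated test.

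- Total expenditure is the named primary endpoint. The 9.7 heading and Section 2.1 conflict with that, no time is decisive, and the spending function is not tied to a single contrast.
- If the heading were used as the decision rule, the one-sided error rate would be about 12% to 40% over assumed correlations from 0.9 to 0, and 25% at 0.5. For expenditure alone at four uncorrected times it would be about 13%, or 5% if the spending function covers them.
- Significance on every metric is not supported. Power is 81% for total expenditure, 72% for all ten primary rows if independent, and 48% to 72% for all 22 rows (correlation 0 to 0.8). These figures take the table's means and spreads as true, with the spread read as an SD, and 51 evaluable per arm.

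The multiplicity point is confined to the Combined protocol and SAP. The separate Protocol makes FACT-G its only primary row and lists these ten rows as exploratory. It repeats the 100% sentence, so the power correction applies there too. The text reviewed does not say which document governs.

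**What to change.** In the Combined protocol and SAP:

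1. In 9.2 and 9.7, name one primary contrast: the difference in mean cumulative total healthcare expenditure from baseline to one prespecified time. Eighteen months is one option, but the choice is the sponsor's. Section 11.2 recommends claims access of between 6 and 18 months, and 9.2 bases the primary analysis on complete cases, so a late time point may lose participants who grant shorter access.
2. In 9.6, tie the spending function and the efficacy boundary to that contrast only. State whether looks are timed from baseline or from trial commencement, and remove the alternative criterion of unspecified health outcomes.
3. Relabel the other nine rows, the cost splits and the other time points as supportive, reported with estimates and confidence intervals and no confirmatory claim. Align 2.1 and the mention of cancer progression in 9.1.
4. In 9.7 of both documents, replace the 100% statements with one saying that, under the tabulated assumptions, power of at least 80% applies to each metric separately.

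These are wording changes, and N stays at 146. The cost is that the sponsor can no longer present a sub-metric result as a primary success. Choosing a late time may also require longer claims access than the current minimum.

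### Combined document, 9.7: 80% power was set metric by metric, so 102 completers do not carry the stated prospect of significance on all primary and secondary metrics (minor; no change to N)

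*Combined protocol and SAP*

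**What the plan says.** Section 9.7 of the Combined protocol and SAP sets "alpha as 0.05 and power of 80% for the one-tail test at enrollment ratio = 1" and describes the calculation as metric-wise. It explains that "the sample size was computed separately for each parameter in the study and the greatest is used to obtain sample size". The largest row needs 102, and the text concludes that a "sample of size of 102 is powerful enough for the analysis to cover 100% of primary and secondary metrics". After allowing for 30% dropout (146 enrolled, 44 lost, 102 left), the last bullet says the trial would be able to reach "statistically significant effects ($p < 0.05$) with respect to 100% of primary and secondary metrics".

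The table lists 10 rows under the primary heading and 12 under the secondary heading. Two rows drive the 102: Total Healthcare Expenditure (10000 vs 8000, "Variance of 4000") and Employee Performance (0.6 vs 0.7, with a spread of 20%). The section gives no joint power and no correlation between metrics.

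**The concern.** Taking the largest of 22 separate sample sizes secures at least the target power for each metric considered alone. It says nothing directly about the chance that all of them reach significance in the same trial. That chance can never exceed the power of the weakest row, and it is usually lower.

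The last bullet moves from the first statement to the second. A reader who takes it at face value would expect a clean sweep if the assumptions are right, and could read an ordinary mixed result as falling short of what the design offered. What is at stake is the accuracy of a stated operating characteristic, not the size or conduct of the trial.

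**Working it through.** **Inputs** (Combined document, 9.7): alpha 0.05, one-tailed, 80% power, 1:1 allocation, 51 completers per arm, and the control value, test value and spread of each row. Correlation between metrics is not given.

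**Step 1: reproduce the plan's figure.** With d = |difference| / spread and a one-sided two-sample t-test:
- Total Healthcare Expenditure: d = 2000/4000 = 0.50, which needs 51 per arm, or 102.
- Employee Performance: d = 0.1/0.2 = 0.50, again 102.
- Dropout: 102/(1 − 0.30) = 145.7, so 146.

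This treats the column headed as a variance as a standard deviation. Read as true variances, the entries would give 1 per arm for expenditure and 248 per arm for performance. The SD reading matches 19 of the 22 rows exactly. The exceptions are planned hospital visits (stated 10, computed 6), prescription expenditure (80 vs 66) and FACT-G (42 vs 46). None of these affects the 102.

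**Step 2: power of each row at 51 per arm.** Power = P(T > t(0.95; 100 df)), where T is noncentral t with noncentrality d × √(51/2).

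| Row | d | Power |
|---|---|---|
| Total Healthcare Expenditure | 0.500 | 80.6% |
| Employee Performance | 0.500 | 80.6% |
| Brief Pain Inventory | 0.571 | 88.9% |
| Prescription expenditure | 0.625 | 93.2% |
| Planned outpatient visits | 0.667 | 95.5% |
| FACT-G, PROMIS, progression (each) | 0.750 | 98.3% |
| GLTEQ | 0.800 | 99.1% |
| Recurrence | 0.900 | 99.8% |
| Other 12 rows | 0.975 or more | at least 99.9% |

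Differences are taken in the intended direction. This matters for GLTEQ, where the table lists control 25 and test 17.

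**Step 3: probability that all 22 are significant.**
- *Upper limit, any dependence:* the power of the weakest row, 80.6%.
- *Lower limit, any dependence:* 1 minus the sum of the shortfalls. In percentage points these are 19.41 + 19.41 + 11.10 + 6.81 + 4.47 + 3 × 1.71 + 0.90 + 0.21, plus about 0.18 for the other 12 rows, or about 67.6. The limit is 32.4%.
- *Independence:* the five weakest rows give 0.8059² × 0.8890 × 0.9319 × 0.9553 = 0.514. The other 17 rows multiply to 0.937. The product is 0.482.
- *Illustration, assumed common correlation (normal model):* 54.6%, 63.3%, 69.0% and 75.1% at 0.2, 0.5, 0.7 and 0.9.

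**Step 4: rows that apply only to a subset.** Section 3 defines presenteeism among employed survivors, but 5.3 does not require employment. The share employed is not given. If 80% of completers were employed (about 41 per arm), Employee Performance would have about 73% power; at 60% (about 31 per arm), about 62%. The progression and recurrence objective is restricted to prostate, lung and colorectal cancers. Those two rows hold 80% only while at least 23 and 16 per arm contribute, which are the table's own figures.

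**The case against.** The strongest reply is that 100% simply means every row's own N is no larger than 102. The section calls the calculation metric-wise and says each N was computed separately. On that reading the sentence about 102 being enough to cover all metrics is defensible, and I do not count it as an error. The last bullet is also softer than a promise: it says the trial would be able to reach significance, not that it will. Both points stand. The last bullet nevertheless speaks of reaching p < 0.05 on all metrics and gives the reader no joint figure.

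A reader might infer that the trial fails unless every metric succeeds, or that it is underpowered. The documents support neither. Section 9.2 places the primary hypothesis on expenditure alone, 9.3 states the secondary hypotheses separately, and the efficacy criterion in 9.6 is joined by *or*. Expenditure itself has 80.6% power on the plan's assumptions.

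A reader might also take 48% to 75% as the joint power. That range rests on an assumed common correlation across very unlike outcomes. Only the 32% and 80.6% limits hold without such an assumption.

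Some rows are open to question: length of stay appears twice, and the synopsis calls the cancer outcomes exploratory. Removing the duplicate and the two cancer rows moves the independence figure only from 48.2% to 49.1%.

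The Protocol's 9.7 carries the same sentence over five primary and secondary rows. Its joint figure under independence is 79.2%, so the numerical gap there is negligible.

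**Conclusion.** The point holds as a minor correction. The last bullet of 9.7 in the Combined document attributes to 102 completers a property that the metric-by-metric calculation does not give. Even on the plan's own figures, at least one of the 22 metrics would miss significance in at least 19.4% of trials (100 − 80.6), and in about 52% (100 − 48.2) if the metrics are independent.

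These figures take the table's differences as true and in the intended direction, use the spreads as SDs, let all 51 per arm contribute to every row, and make no multiplicity adjustment. Smaller numbers on the subset metrics, or any multiplicity adjustment, would lower power further.

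**What to change.** Keep the sentence about 102 covering all metrics, or add that it is meant metric by metric. Replace the final clause of the last bullet with:

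> With 102 completers contributing data, each metric taken singly has about 80% power or more under its assumed difference and spread (one-tailed 5%). This does not imply that all metrics will be significant together; the probability of that is at most about 81%, and about 48% if the metrics are independent. For metrics defined only in a subset (work outcomes in employed survivors; progression and recurrence in prostate, lung and colorectal cancers), power is lower and depends on the number contributing.

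Add one sentence saying that the 80% supporting the trial's conclusion in this document is the figure for its primary endpoint, total healthcare expenditure. The 55% to 75% range need not go into the plan, because its correlation is assumed.

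The cost is a few sentences in 9.7 and a less favourable stated figure. N, data collection and the analyses do not change.
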